4.2 Scientific rationale for study design

A randomized, double-blind, placebo-controlled, parallel-group study design has been selected to demonstrate efficacy and safety of DZP to support regulatory filing. The study population will include study participants 16 years of age and older with moderately to severely active SLE who are receiving stable SOC medication (ie, antimalarials, corticosteroids, and/or immunosuppressants) at screening visit (V1). The primary efficacy outcome measures and other efficacy assessments included in this study are consistent with those used for some other SLE studies and are considered appropriate for establishing efficacy of DZP. Clinically relevant improvement of moderate to severe disease activity over 48 weeks will be used to demonstrate the efficacy of DZP over placebo long term. Early clinically relevant improvement from moderate to severe disease activity will be assessed after 12 and 24 weeks. Long-term disease control will be demonstrated by assessment of flare prevention (flare-free), the achievement of the treat-to-target endpoint LLDAS, and the reduction in SLEDAI-2K score.

4.3 Justification for dose

The selection of the dose is based on the Phase 2b study, SL0023. Efficacy and safety of DZP was assessed in 3 dose arms in SL0023. The lowest dose of 6mg/kg was selected based on non-clinical data on a non-human primate tetanus toxoid (TT) model showing minimal reduction of [REDACTED] titers suggesting some immunomodulation. [REDACTED]
[REDACTED]
[REDACTED]
[REDACTED]
[REDACTED]
[REDACTED].

SL0023 Study participants who received 24mg/kg or 45mg/kg DZP showed overall similar clinical response rates across all clinical endpoints and majority of time points as well as similar reduction in [REDACTED], therefore the 45mg/kg dose is not considered to provide added benefit as compared to the 24mg/kg. This was also applicable in subgroups of participants with higher disease activity and/or more severe disease. While similarities were seen between 24mg/kg and 45mg/kg doses, response rates in study participants receiving 6mg/kg were inconsistent. Moreover, generation of anti-drug antibodies was increased in study participants receiving 6mg/kg as compared to study participants receiving 24mg/kg or 45mg/kg. Therefore, 6mg/kg is considered as a dose with inferior efficacy while 24mg/kg is considered as dose with maximum observed effect. As doses between 6mg/kg and 24mg/kg overlap pharmacokinetically with the 24mg/kg dose, a clear assignment of benefit/risk to dosages below 24mg/kg is difficult. Therefore, in view of the aforementioned information, 24mg/kg was selected as a dose with a maximum effect and an acceptable safety profile.

4.4 End of study definition

A study participant is considered to have completed the study if she/he has completed the Week 48 Visit.

The end of the study is defined as the date of the final visit of the last study participant in the study.

5 STUDY POPULATION

Prospective approval of protocol deviations to recruitment and enrollment criteria, also known as protocol waivers or exemptions, is not permitted.

5.1 Inclusion criteria

Rescreening will be allowed once during the study in case there is new evidence for an inclusion criterion that was not fulfilled at the first screening or in case a study participant no longer meets an exclusion criterion (Section 5.4) or screening period exceeded the maximum duration due to delays in screening processes.

Study participants are eligible to be included in the study only if all of the following criteria apply:

Age

1. Study participant must be ≥ 16 years of age, unless restricted by local regulation, at the time of signing the Informed Consent form (ICF).

Type of participant and disease characteristics

2. Study participants who have moderate to severe disease activity due to either persisting active SLE or due to an acute worsening of SLE in the scope of frequent flaring/relapsing-remitting SLE despite stable SOC medication defined as:

- a1. Diagnosed with SLE at least 24 weeks before the Screening Visit (Visit 1) by a qualified physician (eg, rheumatologist, internal medicine expert, nephrologist, or dermatologist)
- b. Classified by 2019 SLE European League Against Rheumatism/American College of Rheumatology (EULAR/ACR) classification criteria for SLE
- c1. With serological evidence for SLE at Screening as demonstrated by at least 1 of the following:
 - i) Evidence for [REDACTED] (defined as evidence for [REDACTED] in central laboratory)
 - ii) Either [REDACTED] < lower limit of normal (LLN) OR [REDACTED] < LLN OR elevated erythrocyte-bound complement [REDACTED] (where available) as measured by central laboratory
 - iii) [REDACTED] with a titer of at least 1:80 confirmed by central laboratory in combination with evidence of at least 1 of the following SLE typical autoantibodies:
 1. [REDACTED] (central laboratory)

2. [REDACTED] (central laboratory)

3. Historic evidence for anti-dsDNA antibodies (at least 2 historical positive tests [$>\text{upper limit of normal (ULN)}$ of lab assay with an interval of at least 12 weeks between tests])

d. Moderately to severely active defined as

- British Isles Lupus Assessment Group Disease Activity Index 2004 (BILAG 2004) Grade B in ≥ 2 organ systems and/or a BILAG 2004 Grade A in ≥ 1 organ systems at Screening and Baseline Visit AND
- SLEDAI-2K ≥ 6 at Screening Visit AND
- SLEDAI-2K without labs ≥ 4 at Baseline Visit

e3. Receiving the following SOC medication at stable dose:

- Antimalarial treatment in combination with corticosteroids and/or immunosuppressants or as stand-alone treatment if justified (ie, if for other SLE SOC medications there is documented intolerance in medical history, documented lack of efficacy, contraindications, or lack of availability) OR
- Treatment with corticosteroids and/or immunosuppressants if anti-malarial treatment is not possible (ie, documented intolerance in medical history or antimalarials not available locally)

Stable dose is defined for:

- Antimalarials as no change to dose within 8 weeks prior to Screening and during Screening Period and a start date at least 12 weeks before Screening. Maximum doses are described in Section 6.5.1.2.
- Corticosteroids as no change in dose for 2 weeks prior to Screening, no change during Screening Period, and no iv pulse therapy ($>500\text{mg} \times 1$ to 3 days) within 4 weeks prior to screening. The maximum dose allowed at screening is 40mg/day prednisone or equivalent (see Section 6.5.1.1).
- Immunosuppressants as no change in dose for 12 weeks prior to Screening Visit and during Screening Period. Maximum doses are described in Section 6.5.1.3.

Weight

3. Body weight $\geq 40\text{kg}$ and $\leq 160\text{kg}$.

Sex

4a. Female and/or male

- A male study participant must agree to use contraception, as detailed in Section 10.4, during the Treatment Period and for at least 17 weeks after the final dose of study medication and refrain from donating sperm during this period.
- A female study participant is eligible to participate if she is not pregnant, not breastfeeding (including pumping breast milk to feed to a child), and at least 1 of the following conditions applies:

- Not a woman of childbearing potential (WOCBP) as defined in Section 10.4 of the protocol, or
- A WOCBP who agrees to follow the contraceptive guidance in Section 10.4 of the final protocol during the treatment period and for at least 17 weeks after the final dose of study medication.

Informed consent

5. Capable of giving signed informed consent as described in Section 10.1.3, which includes compliance with the requirements and restrictions listed in the ICF and in this protocol.

5.2 Exclusion criteria

Study participants are excluded from the study if any of the following criteria apply:

Medical conditions

General

1. Study participant has any medical or psychiatric condition (including conditions due to neuropsychiatric SLE) that, in the opinion of the Investigator, could jeopardize or would compromise the study participant's ability to participate in this study. This includes study participants with a life threatening condition (eg, CTCAE grade 4 conditions, CAPS, acute severe renal failure, acute severe central nervous system [CNS] manifestations)
- 2a. Study participant has moderate to severe disease activity (as defined per inclusion criterion 2.d) at the Screening Visit (V1) due to an acute flare but **does not fulfill at least one** of the following criteria in addition to the Screening Visit:
 - ≥1 additional disease flare within the last 24 weeks prior to Screening (as per medical record) OR
 - [REDACTED] positivity in combination with [REDACTED] <LLN as per central laboratory OR
 - [REDACTED] <LLN as per central laboratory OR
 - African-American OR
 - Age <25 years
3. Study participant has a history of chronic alcohol or drug abuse within the previous 24 weeks.
4. Study participant has a known [REDACTED] to any components of DZP including PEG or comparative drugs (and/or an investigational device) as stated in this protocol.
- 5a. Study participant has a history of an anaphylactic reaction to parenteral administration of contrast agents, human or murine proteins, or monoclonal antibodies. This includes systemic reactions due to latex allergy.
- 6a. Study participant has a history of malignancy, except the following treated cancers: cervical carcinoma in situ (after complete resection [eg, curettage, electrodesiccation] not later than 4 weeks prior to the Screening Visit [V1]), basal cell carcinoma, or dermatological

squamous cell carcinoma (after complete resection not later than 24 weeks prior to the Screening Visit [V1]).

7. Study participants who have had major surgery (including joint surgery) within the 24 weeks prior to Screening, or planned surgery within 24 weeks after entering the study.
8. Study participants who have had significant blood loss or have donated or received 1 or more units (450mL) of blood within 30 days prior to the Screening Visit or have donated plasma or platelets within 14 days prior to the Screening Visit.
9. Study participants with a history of thromboembolic events within 52 weeks of Screening (Visit 1), including but not limited to the following: deep venous thrombosis, pulmonary embolism, cortical sinus thrombosis, myocardial infarction, stroke, transient ischemic attack, or arterial insufficiency causing digital gangrene or tissue necrosis.

Note:

- 1) In case of anti-phospholipid antibodies present at the Screening Visit, a prophylactic treatment should be considered in line with local or international guidelines and considering the individual risk profile of the patient for thromboembolic events
- 2) Study participants with antiphospholipid syndrome (APS) can be enrolled if they are on stable anticoagulation therapy at an effective dose (eg, International Normalized Ratio [INR] target 2 to 3 depending on clinical situation) and did not have a thromboembolic event and/or obstetric morbidity within the 52 weeks prior to Screening (Visit 1).Obstetric morbidity is defined as 1 or more unexplained deaths of a morphologically normal fetus at or beyond the tenth week of gestation with the latest incidence within 52 weeks prior to Screening (Visit 1) OR 1 or more preterm births of a morphologically normal neonate before the 34th week of: (i) eclampsia or severe pre-eclampsia or (ii) recognized features of placental insufficiency with the latest incidence within 52 weeks prior to Screening (Visit 1).
10. Study participants with a history of catastrophic APS or saddle pulmonary embolism.
- 11a. Study participant has an increased risk for thromboembolic events due to an ongoing heart disease or due to a medical device, including but not limited to vascular graft, valvular heart disease, atrial fibrillation, or a heart rhythm disorder.
12. Study participant has a BILAG 2004 Grade A in the musculoskeletal system due to severe arthritis only AND no BILAG 2004 Grade A or B in any other organ system AND no current (within the past 4 weeks) evidence for synovitis based on imaging methods such as magnetic resonance imaging or doppler-sonography.
- 13a. Study participant has a mixed connective tissue disease, scleroderma, and/or overlap syndrome of these diseases with SLE.
 - Clarification: Study participants with rheumatoid arthritis in their medical history are not considered as having an overlap syndrome and are therefore eligible.
14. Study participant has evidence of human immunodeficiency virus infection, agammaglobulinemias, T-cell deficiencies, or human T-cell lymphotropic virus-1 infection at any time prior to or during the study.

15a. Study participant has clinically significant active or latent infection (eg, chronic viral hepatitis B or C, or SARS CoV-2 infection [see Section 8.2.7]).

16a. Study participant has a history of a serious infection within the last 60 days prior to the first study medication infusion (Visit 2) that required iv/intramuscular antibiotics, systemic antiviral treatment or required hospitalization/prolonged hospitalization. Study participants must have completed any prior anti-infective therapy for serious infections prior to the first study medication infusion.

17b. Study participant had a reactivated latent infection (eg, cytomegalovirus, herpes simplex virus, or herpes zoster infection) or opportunistic infection (including but not limited to pneumocystis, cytomegalovirus, or severe herpes zoster infection) within 12 weeks prior to the first study medication infusion (Visit 2), or is currently receiving suppressive therapy for an opportunistic infection.

18. Study participant has a clinically relevant recurrent (more than 3 times a year) infection.

19. Study participant with any of the following tuberculosis (TB) exclusion criteria:

- Known active TB infection.
- History of active TB infection involving any organ system or findings in other organ systems consistent with TB, unless adequately treated according to WHO/CDC therapeutic guidance and proven to be fully recovered upon consult with a TB specialist.
- Latent TB infection (LTBI) unless appropriate prophylaxis is initiated at least 4 weeks prior to study medication dosing and will be continued to completion of prophylaxis.
- High risk of acquiring TB infection, eg, known close exposure to another person with active TB infection within 3 months prior to Screening or significant time spent in a health care delivery setting or institution where individuals infected with TB are housed and where the risk of transmission is high within 3 months prior to Screening.
- Current nontuberculous mycobacterial (NTM) infection or history of NTM infection unless proven to have fully recovered upon consult with a TB specialist.

20a. Study participants who have received live/live attenuated vaccines within 6 weeks prior to the first study medication infusion (Visit 2) or who plan to receive these vaccines during the study or up to 12 weeks after the final dose of study medication will be excluded. Use of nonlive vaccines is allowed during the study; however, based on current evidence, it cannot be excluded that the effectiveness of these vaccines may be compromised by the study medication. Investigator should consider local and international guidance on vaccination in immunosuppressed patients and discuss risks, benefits and administration options with participants (for more details see also Section 6.6.1 and Section 8.2.7).

Prior/Concomitant therapy

21. Study participant has active lupus that, in the opinion of the Investigator or according to local or international guidances, requires an increase in SOC therapy outside of that permitted in Section 6.5.1.

22. Study participants requiring plasma exchange or immunoabsorption in the 16 weeks prior to Visit 2 or at any time during the study.

23. Study participant has used the prohibited medications listed in [Table 6-7](#), regardless of route (with the exception of eye drops), within the time frame (Wash-Out Period) listed in the table prior to Screening (Visit 1). Study participant has used investigational agents not included in [Table 6-7](#), including other investigational or recently approved biologics, off-label use of immunomodulators, or device products, within 12 weeks or 5 times the half-life prior to Screening (Visit 1), whichever is longer. Concomitant participation in studies where no product or device is administered/used may be allowed if discussed and approved by the Medical Monitor/UCB. If there are any questions regarding acceptable wash-out periods not mentioned, the Investigator should contact the Medical Monitor.

24. Hormone replacement therapy is allowed provided it is not initiated within the 4 weeks prior to Screening (Visit 1) or during the study. The hormone replacement therapy may be decreased and/or discontinued at any time during the study.

25. Study participant should, if possible, stay on stable doses of the following other concomitant medications for the treatment of SLE during the study unless changes in these treatments are clinically indicated: analgesics, non-steroidal anti-inflammatory drugs (NSAIDs), 3-hydroxy-3-methyl-glutaryl-coenzyme A (HMG-CoA) reductase inhibitors (statins), angiotensin converting enzyme (ACE) inhibitors, and other anti-hypertensive drugs.

Prior/Concurrent clinical study experience

26a. Study participant has previously been randomized within this study or has previously been assigned to treatment with DZP in a study evaluating DZP.

27. Study participant has participated in another study of an IMP (and/or an investigational device) within the previous 12 weeks or 5 half-lives of the IMP whatever is longer (see [Table 6-7](#)) or is currently participating in another study of an IMP.

Diagnostic assessments

28a. Study participant has history of a suicide attempt within the 5 years prior to the Screening Visit or has had suicidal ideation in the past 6 months as indicated by a positive response ("Yes") to either Question 4 or Question 5 of the "Screening/Baseline" version of the Columbia Suicide Severity Rating Scale (C-SSRS) at Screening.

Note:

- In case a study participant responds to Question 9 in Patient Health Questionnaire-9 (PHQ-9) [REDACTED] the severity of [REDACTED] the suicidal ideation needs to be adequately assessed with the C-SSRS rating scale.

– In case of history of a suicide attempt more than 5 years ago the absence of concurrent suicidal ideation and/or severe depression should be confirmed by a mental healthcare practitioner before enrolling into the study.

29a. Study participant has ≥ 3 times the ULN alanine aminotransferase (ALT), aspartate aminotransferase (AST), or alkaline phosphatase (ALP), or $>$ ULN bilirubin ($\geq 1.5 \times$ ULN

bilirubin if known Gilbert's syndrome), except in the case where the abnormal test values are ascribed to SLE hepatitis

- If study participant only has >ULN, but <1.5xULN bilirubin, fractionate bilirubin to identify possible undiagnosed Gilbert's syndrome (ie, direct bilirubin<35%) should be assessed, except in the case where the abnormal test values are ascribed hemolytic anemia, in the opinion of the Investigator.
- In case of a suspected SLE hepatitis, eligibility must be discussed with the Medical Monitor.
- If study participant has a result of ALT, AST, or ALP that is >ULN but that does not meet the exclusion limit at Screening, a repetition of the lab assessment is recommended to judge the dynamic of the increase, but is in the Investigator's discretion, considering the medical history of the participant. In case of a further clinically relevant increase (with a value that still doesn't meet the exclusion limit), inclusion of the study participant must be discussed with the Medical Monitor.

30a. Study participant has chronic kidney failure stage 4, manifested by estimated glomerular filtration rate (eGFR) <30mL/min/1.73m², or serum creatinine >2.5mg/dL, or participant has proteinuria >3g/day, or protein:creatinine ratio >340mg/mmol at the Screening Visit.

31a. Study participant has any significant hematologic abnormalities at the Screening Visit (Visit 1) as follows:

- a. Hemoglobin <7.0g/dL
- b. █ T-lymphocytes <200/mm³
- c. Absolute neutrophil count <500/mm³
- d. █ T lymphocytes <500/mm³ in combination with neutrophil count <1000/mm³
- e. Platelets <25,000/mm³. Study participants with a higher platelet count should also be excluded if they have a clinical risk of bleeding for reasons other than SLE.

Note: Study participants with an isolated laboratory parameter outside of the normal range at the Screening Visit may have a repeat test. If the repeat laboratory parameter is within normal range, the study participant may be randomized at the Baseline Visit, provided they meet all other eligibility criteria.

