8.1 Efficacy assessments

8.1.1 Clinical assessments of disease activity

8.1.1.1 BILAG 2004

The BILAG 2004 will be used as a clinical assessment of SLE disease activity (Tsokos et al, 2007).

The Investigators will perform an anamnesis and physical examination at every visit and will record present symptoms corresponding to the BILAG 2004 components in the electronic clinical outcomes assessment (eCOA). Clinical features attributable to SLE are to be recorded and based on the study participant's condition in the last 4 weeks compared with the previous 4 weeks. For vital signs and laboratory parameters, Investigators must indicate whether or not values are outside the normal range and, if outside the normal range, whether or not they are due to SLE.

Nine body/organ-based systems will be assessed if SLE symptoms are present:

- Constitutional (fatigue, fever, anorexia, weight loss, etc)
- Mucocutaneous (rash, alopecia, mucosal ulcers, etc)
- Neuropsychiatric (headache, seizure, psychosis, etc)
- Musculoskeletal [REDACTED] etc)
- Cardiorespiratory (coronary vasculitis, cardiac failure, effusion, etc)
- Gastrointestinal (lupus enteritis, hepatitis, peritonitis, etc)
- Ophthalmic (keratitis, scleritis, optic neuritis, etc)
- Renal (proteinuria, urine microscopy for red blood cells, casts, etc)
- Hematology (cytopenias, coagulopathy, etc)

The Investigator must maintain/provide independent supporting source documents (eg, chart, worksheet, clinic notes, labs, and photodocumentation of cutaneous SLE manifestations) capable of withstanding audit:

- For each SLE symptom present at the visit or present within the past 4 weeks before the visit
- Indicating if symptom had a new onset, was improving, same, or worse in the past 4 weeks as compared to the prior 4 weeks
- Sufficient descriptive detail to support changes (improved, worsening); eg, number/location of arthritic joints, size/location of rashes, etc
- Information indicating that other symptoms relevant for BILAG were not present at the time point of the visit and within the 4 weeks prior to the visit

[figure not shown]
The Sponsor will provide centralized grading (A, B, C, D, and E) based on BILAG 2004 eCOA pages completed by the Investigator, eCRF pages completed by Investigators, laboratory parameters, and may be subject to adjudication. Prior to Visit 2, the site must have received

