9.6 Handling of dropouts or missing data

As the primary efficacy variable is treatment responder rate in BICLA at Week 48, the handling of missing data, dropouts and intercurrent events is described as follows.

- In case of the use of escape treatment as an intercurrent event prior to the Week 48 Visit (ie, the escape treatment initiation is at least 1 day before), study participants will be included for the primary analysis as non-responders per the composite strategy handling of this intercurrent event.
- Study participants who prematurely withdraw from the study or permanently discontinue study medication prior to the Week 48 Visit, will be included for the primary analysis as non-responders per the composite strategy handling of this intercurrent event.
- Study participants who have a missing BICLA response for the Week 48 assessment for any other reason besides defined intercurrent events will be imputed as non-responders for the primary efficacy analysis.

- A modified non-responder imputation (mNRI) for missing data will be applied to its components, in order to obtain the BICLA response. If the Week 48 assessment was performed but the value for a single component (BILAG 2004, SLEDAI-2K, or PGA) is not available, then the missing component value will be imputed from the respective previous visit value prior to computing the BICLA treatment response variable (limited to 1 visit back). In the case where the predose laboratory result is missing (at Screening and at Baseline and there is no other unscheduled predose laboratory result), the BILAG 2004 body/organ system Baseline score for the body system requiring the missing laboratory result will be set to a score of BILAG 2004 D level disease. More details will be included in the SAP.

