10.6 Appendix 6: Liver safety – suggested actions and follow-up assessments

Participants with potential drug-induced liver injury must be assessed to determine if study medication must be discontinued. In addition, all concomitant medications and herbal supplements that are not medically necessary should also be discontinued.

Investigators should attempt to obtain information on study participants in the case of study medication discontinuation to complete the final evaluation.

Study participants with potential drug-induced liver injury should not be withdrawn from the study until investigation and monitoring are complete. All results of these evaluations and observations, as well as the reason(s) for study medication discontinuation and/or participant withdrawal (if applicable), must be recorded in the source documents. The eCRF must document the primary reason for discontinuation of study medication.

A specific monitoring plan must be agreed between the UCB study physician and the Investigator for study participants who have ALT >5 ULN. The monitoring plan should include any necessary follow-up assessments (until resolution of the abnormal lab values).

Table 10-1: Phase 3-4 liver chemistry stopping criteria and follow-up assessments

Liver Chemistry Stopping Criteria	
ALT-absolute	ALT \geq 8xULN
ALT Increase	ALT \geq 5xULN but $<$ 8xULN persists for \geq 2 weeks ALT \geq 3xULN but $<$ 5xULN persists for \geq 4 weeks
Bilirubin^{a,b}	ALT \geq 3xULN and bilirubin \geq 2xULN ($>$ 35% direct bilirubin)
INR^b	ALT \geq 3xULN and international normalized ratio (INR) $>$ 1.5, if INR measured
Cannot Monitor	ALT \geq 5xULN but $<$ 8xULN and cannot be monitored weekly for \geq 2 weeks ALT \geq 3xULN but $<$ 5xULN and cannot be monitored weekly for \geq 4 weeks
Symptomatic^c	ALT \geq 3xULN associated with symptoms (new or worsening) believed to be related to liver injury or [REDACTED]
Suggested Actions and Follow up Assessments	
Actions	

• Immediately discontinue study medication.• Report the event to the UCB within 24 hours.• Complete the liver event case report form (eCRF), and complete a serious adverse event (SAE) data collection tool if the event also met the criteria for an SAE.^b• Perform liver chemistry follow-up assessments.	
Follow Up Assessments	

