
^a Serum bilirubin fractionation should be performed if testing is available. If serum bilirubin fractionation is not immediately available, discontinue study medication if ALT $\geq 3\times$ ULN **and** bilirubin $\geq 2\times$ ULN. Additionally, if serum bilirubin fractionation testing is unavailable, **record the absence/presence of detectable urinary bilirubin on dipstick** which is indicative of direct bilirubin elevations suggesting liver injury.

^b All events of ALT $\geq 3\times$ ULN and bilirubin $\geq 2\times$ ULN ($>35\%$ direct bilirubin) or ALT $\geq 3\times$ ULN and INR >1.5 may indicate severe liver injury (**possible 'Hy's Law'**) and must be reported as an SAE (excluding studies of

hepatic impairment or cirrhosis). The INR measurement is not required and the stated threshold value will not apply to participants receiving anticoagulants.

^c New or worsening symptoms believed to be related to liver injury (such as fatigue, nausea, vomiting, right upper quadrant pain or tenderness, or jaundice) or [REDACTED] (such as fever, rash or eosinophilia).

^d Includes: Hepatitis A [REDACTED]; HBsAg and HBcAb; hepatitis C RNA; cytomegalovirus [REDACTED] Epstein-Barr viral capsid antigen [REDACTED] (or if unavailable, heterophile antibody or monospot testing); and hepatitis E [REDACTED]

^e If hepatitis delta antibody assay cannot be performed, it can be replaced with a polymerase chain reaction (PCR) of hepatitis D RNA virus (where needed) (Le Gal, 2005).

^f PK sample may not be required for participants known to be receiving placebo or non-comparator interventions. Record the date/time of the PK blood sample draw and the date/time of the last dose of study medication prior to the PK blood sample draw on the eCRF. If the date or time of the last dose is unclear, provide the participant's best approximation. If the date/time of the last dose cannot be approximated OR a PK sample cannot be collected in the time period indicated above, do not obtain a PK sample. Instructions for sample handling and shipping are in the Laboratory Manual.

This document cannot be used to support any marketing application and any extensions or variations thereof.
PUBLIC COPY

10.7 Appendix 7: Medical device AEs, ADEs, SAEs and device deficiencies: definition and procedures for recording, evaluating, follow-up, and reporting

Not applicable.

This document cannot be used to support any marketing authorization application and any extensions or variations thereof.

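### Criterion 29a admits participants with raised ALT from SLE hepatitis, but the Table 10-1 liver stopping rows take no account of Baseline or of that waiver

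*Protocol*

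**What the plan says.** **Entry.** Protocol 5.2, criterion 29a (repeated in Appendix 13), excludes ALT, AST or ALP of at least 3xULN, or bilirubin above ULN, "except in the case where the abnormal test values are ascribed to SLE hepatitis". The criterion adds: "In case of a suspected SLE hepatitis, eligibility must be discussed with the Medical Monitor". It gives no numerical ceiling for waived values. Hepatitis belongs to the disease activity being scored: Section 8.1.1.1 lists it in a BILAG organ system, "Gastrointestinal (lupus enteritis, hepatitis, peritonitis, etc").

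**Stopping.** Appendix 6, Table 10-1, lists these rows:
- ALT at least 8xULN
- ALT 5 to <8xULN for at least 2 weeks
- ALT 3 to <5xULN for at least 4 weeks
- ALT at least 3xULN together with bilirubin at least 2xULN (more than 35% direct), INR above 1.5, or symptoms
- either of the two ALT bands above, if weekly monitoring is not possible

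The first action is "Immediately discontinue study medication", under an appendix titled "suggested actions and follow-up assessments". Section 7.1.1 asks the Investigator to consider discontinuation. Section 7.1.3, item 4, requires permanent discontinuation when potential drug-induced liver injury is judged related to study medication.

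**Analysis and reporting.** Section 9.6 counts as non-responders "Study participants who prematurely withdraw from the study or permanently discontinue study medication prior to the Week 48 Visit". Notes in Appendix 2 and under Table 10-1 require all events of ALT at least 3xULN with bilirubin at least 2xULN (more than 35% direct) to be reported as SAEs. Appendix 3 does not treat SLE-related laboratory findings as AEs unless they are serious. SAP 10.3 plans a table and listing of participants meeting the potential drug-induced liver injury criteria, by reference to Figure 7-1.

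**The concern.** The protocol deliberately admits people whose liver tests are abnormal because of lupus, then applies liver thresholds that suit participants who start near normal. Read literally, Table 10-1 can tell a site to stop study medication for unchanged disease that the same protocol accepted at entry.

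Three things are at stake:
- **Conduct.** Two sites with identical participants could act differently, one following the table's action line and the other Section 7.1.1.
- **Primary endpoint.** If a stop becomes permanent, the participant is a BICLA non-responder whatever the lupus does.
- **Safety interpretation.** Pre-existing lupus hepatitis can appear in the drug-induced liver injury table or be reported as an SAE. Such displays are usually small, so one or two misattributed cases can change how they read.

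The protocol makes allowances of this kind elsewhere. QTcF limits in bundle branch block depend on the Baseline value (Section 7.1.2), and the INR limit is lifted for anticoagulant users (notes to Table 10-1). The group that 29a admits with abnormal liver tests has no counterpart.

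**Working it through.** **1. Entry against stopping, with ALT unchanged after admission under 29a**

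| ALT at entry (xULN) | Row met on ALT alone | When | With bilirubin ≥2xULN, >35% direct |
|---|---|---|---|
| 2.9 | none | – | none |
| 3 or 4 | 3 to <5 for ≥4 weeks | 4 weeks | met at once |
| 5 or 7 | 5 to <8 for ≥2 weeks | 2 weeks | met at once |
| 8 or 10 | ≥8, no persistence needed | first test | met at once |

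Every waived entrant whose ALT stays at or above 3xULN therefore meets a row within 4 weeks without any rise. The table does not say whether the persistence clock may include Screening. In Appendix 6, Baseline appears only as an end point for follow-up monitoring, not in any stopping row.

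**2. Who is affected.** Each row requires ALT at or above 3xULN. Entrants waived for AST, ALP or bilirubin alone meet no row at entry.

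**3. From meeting a row to non-response.** Three steps are needed:
- Medication must actually be stopped. The Table 10-1 action says so; Section 7.1.1 and the Appendix 6 introduction call for consideration and assessment.
- The stop must become permanent. Appendix 6 allows a restart only if the protocol permits it and the sponsor approves; otherwise discontinuation is permanent. Section 7.1.3 separately allows interruption for a laboratory abnormality, with restart after consultation.
- Section 9.6 then assigns non-response.

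**4. SAE note against AE definitions.** The note covers all events of the ALT-plus-bilirubin pattern and excepts only hepatic impairment or cirrhosis studies. Appendix 3 excludes SLE-related laboratory findings unless serious and says that an event that is not an AE cannot be an SAE. Section 8.3.1 points to events that are new, recurrent or worse since the initial visit. Appendix 3 also names potential Hy's law as an example of an important medical event, and Section 8.3.6 defines that term as having no alternative explanation. Whether known SLE hepatitis counts as such an explanation is not stated.

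**5. Size.** The documents give no frequency of SLE hepatitis at entry. If 1% to 3% of the 312 planned participants entered under the waiver (an assumption), that is 0.01 × 312 = 3.1 to 0.03 × 312 = 9.4, or about 3 to 9. Those meeting a row would be fewer, since ALT must be raised and stay raised.

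For power, the plan's figure comes first: two-sided Fisher exact test, alpha 0.05, 104 versus 208 participants, response 0.32 versus 0.52. Exact enumeration gives 0.911, consistent with the stated 90%. Now let a fraction f of would-be responders in both arms become non-responders by this route, so that the rates are 0.32(1−f) and 0.52(1−f):

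| f (assumed) | Power |
|---|---|
| 0.005 | 0.909 |
| 0.01 | 0.906 |
| 0.02 | 0.901 |
| 0.03 | 0.896 |

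At f = 0.03 the rates are 0.3104 and 0.5044. Even this reduces power by only 0.015.

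**The case against.** The strongest reply is that nobody has to be stopped. Section 7.1.1 is discretionary, Section 7.1.3 ties mandatory permanent discontinuation to relatedness, and Appendix 6 presents its actions as suggestions. Unchanged lupus hepatitis judged unrelated need not lead to discontinuation. Uniform ULN-based limits with clinical judgement may also be a deliberate, cautious choice. This stands to the extent that a reader might infer that waiver entrants must be stopped and become non-responders; the documents do not support that. It does not remove the conflict, because none of the softer passages mentions 29a or a raised Baseline, and the table's action line is unqualified.

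A reader might also infer that setting the table aside would leave these participants unprotected. That is not so. Appendix 6 requires an agreed monitoring plan when ALT exceeds 5xULN, Section 7.1.1 allows stopping in the participant's interest, 29a requires the Medical Monitor discussion, and exclusion criterion 1 covers life-threatening conditions such as CTCAE grade 4.

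Nor should one infer that lupus hepatitis will fill the Hy's law category. The definition in Section 8.3.6 and SAP 10.1 requires that there be no alternative explanation. SAP 10.3 also lists all laboratory data with change from Baseline, so a raised starting value can be seen in the listings, though the described table does not separate it.

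Finally, Figure 7-1, to which Section 7.1.1 and SAP 10.3 refer, is not reproduced in the text available here, and parts of the SAP are redacted. An allowance there cannot be excluded. If Figure 7-1 contains one, Table 10-1 should agree with it.

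**Conclusion.** The point holds in a limited form. For participants admitted under 29a with ALT at or above 3xULN, the entry criterion and Table 10-1 conflict: unchanged disease is enough to meet a stopping row at entry or within 2 to 4 weeks, and the passages differ on what follows. The SAE note has a similar unresolved tension with Appendix 3. Discontinuation and BICLA non-response are possible consequences, not necessary ones.

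The number affected is unknown; 3 to 9 waiver entrants is only an illustration from an assumed 1% to 3%, and an upper bound on those meeting a row under that assumption. Power is essentially untouched. The weight lies in consistent conduct and in reading the liver safety table. Priority is minor to moderate. The conclusion rests on the legible rows and notes of Table 10-1 and would be narrowed if Figure 7-1 already addresses a raised Baseline.

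**What to change.** **Protocol.** Reconcile criterion 29a with Sections 7.1.1 and 7.1.3, Figure 7-1, Table 10-1 and the SAE notes (Appendix 2 and Appendix 6). State how each applies to a participant admitted under the SLE-hepatitis waiver, including whether a pattern already present before dosing is reportable as an SAE. Any threshold or stopping rule for this group is the sponsor's clinical decision; this review proposes none.

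**SAP 10.3.** Flag participants admitted under the waiver, and show the potential drug-induced liver injury table with and without them.

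**Cost.** One short protocol clarification, one derived flag and one extra display. The sample size and primary analysis do not change.
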